14.1.3.2 Time to event variables

The protocol should state which of the following variables is used in that study.

14.1.3.2.1 Progression-free survival

Usually in all Oncology studies, patients are followed for tumor progression after discontinuation of study medication for reasons other than progression or death. If this is not used, e.g. in Phase I or II studies, this should be clearly stated in the protocol. Note that randomized trials (preferably blinded) are recommended where PFS is to be the primary endpoint.

Progression-free survival (PFS) is the time from date of randomization/start of treatment to the date of event defined as the first documented progression or death due to any cause. If a patient has not had an event, progression-free survival is censored at the date of last adequate tumor assessment.

14.1.3.2.2 Overall survival

All patients should be followed until death or until patient has had adequate follow-up time as specified in the protocol whichever comes first. The follow-up data should contain the date the patient was last seen alive / last known date patient alive, the date of death and the reason of death (“Study indication” or “Other”).

Overall survival (OS) is defined as the time from date of randomization/start of treatment to date of death due to any cause. If a patient is not known to have died, survival will be censored at the date of last known date patient alive.

14.1.3.2.3 Time to progression

Some studies might consider only death related to underlying cancer as an event which indicates progression. In this case the variable “Time to progression” might be used. TTP is defined as PFS except for death unrelated to underlying cancer.

Time to progression (TTP) is the time from date of randomization/start of treatment to the date of event defined as the first documented progression or death due to underlying cancer. If a patient has not had an event, time to progression is censored at the date of last adequate tumor assessment.

14.1.3.2.4 Time to treatment failure

This endpoint is often appropriate in studies of advanced disease where early discontinuation is typically related to intolerance of the study drug. In some protocols, time to treatment failure may be considered as a sensitivity analysis for time to progression. The list of discontinuation reasons to be considered or not as treatment failure may be adapted according to the specificities of the study or the disease.

Time to treatment failure (TTF) is the time from date of randomization/start of treatment to the earliest of date of progression, date of death due to any cause, or date of discontinuation due to reasons other than ‘Protocol violation’ or ‘Administrative problems’. The time to treatment failure for patients who did not experience treatment failure will be censored at last adequate tumor assessment.

14.1.3.2.5 Duration of response

The analysis of the following variables should be performed with much caution when restricted to responders since treatment bias could have been introduced. There have been reports where a treatment with a significantly higher response rate had a significantly shorter duration of response but where this probably primarily reflected selection bias which is explained as follows: It is postulated that there are two groups of patients: a good risk group and a poor risk group. Good risk patients tend to get into response readily (and relatively quickly) and tend to remain in response after they have a response. Poor risk patients tend to be difficult to achieve a response, may have a longer time to respond, and tend to relapse quickly when they do respond. Potent agents induce a response in both good risk and poor risk patients. Less potent agents induce a response mainly in good risk patients only. This is described in more detail by [Morgan \(1988\)](#).

It is recommended that an analysis of all patients (both responders and non-responders) be performed whether or not a “responders only” descriptive analysis is presented. An analysis of responders should only be performed to provide descriptive statistics and even then interpreted with caution by evaluating the results in the context of the observed response rates... If an inferential comparison between treatments is required this should only be performed on all patients (i.e. not restricting to “responders” only) using appropriate statistical methods such as the techniques described in [Ellis et al \(2008\)](#). It should also be stated in the protocol if duration of response is to be calculated in addition for unconfirmed response.

For summary statistics on “responders” only the following definitions are appropriate. (Specific definitions for an all-patient analysis of these endpoints are not appropriate since the status of patients throughout the study is usually taken into account in the analysis).

Duration of overall response (CR or PR): For patients with a CR or PR (which may have to be confirmed the start date is the date of first documented response (CR or PR) and the end date and censoring is defined the same as that for time to progression.

The following two durations might be calculated in addition for a large Phase III study in which a reasonable number of responders is seen.

Duration of overall complete response (CR): For patients with a CR (which may have to be confirmed) the start date is the date of first documented CR and the end date and censoring is defined the same as that for time to progression.

Duration of stable disease (CR/PR/SD): For patients with a CR or PR (which may have to be confirmed) or SD the start and end date as well as censoring is defined the same as that for time to progression.

14.1.3.2.6 Time to response

Time to overall response (CR or PR) is the time between date of randomization/start of treatment until first documented response (CR or PR). The response may need to be confirmed depending on the type of study and its importance. Where the response needs to be confirmed then time to response is the time to the first CR or PR observed.

Although an analysis on the full population is preferred a descriptive analysis may be performed on the “responders” subset only, in which case the results should be interpreted with caution and in the context of the overall response rates, since the same kind of selection bias may be introduced as described for duration of response in [Section 14.1.3.2.5](#). It is recommended that an analysis of all patients (both responders and non-responders) be performed whether or not a “responders only” descriptive analysis is presented. Where an inferential statistical comparison is required, then all patients should definitely be included in the analysis to ensure the statistical test is valid. For analysis including all patients, patients who did not achieve a response (which may have to be a confirmed response) will be censored using one of the following options.

- at maximum follow-up (i.e. FPFV to LPLV used for the analysis) for patients who had a PFS event (i.e. progressed or died due to any cause). In this case the PFS event is the worst possible outcome as it means the patient cannot subsequently respond. Since the statistical analysis usually makes use of the ranking of times to response it is sufficient to assign the worst possible censoring time which could be observed in the study which is equal to the maximum follow-up time (i.e. time from FPFV to LPLV)
- at last adequate tumor assessment date otherwise. In this case patients have not yet progressed so they theoretically still have a chance of responding

Time to overall complete response (CR) is the time between dates of randomization/start of treatment until first documented CR. Similar analysis considerations including (if appropriate) censoring rules apply for this endpoint described for the time to overall response endpoint.

14.1.3.2.7 Definition of start and end dates for time to event variables

Assessment date

For each assessment (i.e. evaluation number), the **assessment date** is calculated as the latest of all measurement dates (e.g. X-ray, CT-scan) if the overall lesion response at that assessment is CR/PR/SD/UNK. Otherwise - if overall lesion response is progression - the

assessment date is calculated as the earliest date of all measurement dates at that evaluation number.

Start dates

For all “time to event” variables, other than duration of response, the randomization/ date of treatment start will be used as the start date.

For the calculation of duration of response the following start date should be used:

- Date of first documented response is the assessment date of the first overall lesion response of CR (for duration of overall complete response) or CR / PR (for duration of overall response) respectively, when this status is later confirmed.

End dates

The end dates which are used to calculate ‘time to event’ variables are defined as follows:

- Date of death (during treatment as recorded on the treatment completion page or during follow-up as recorded on the study evaluation completion page or the survival follow-up page).
- Date of progression is the first assessment date at which the overall lesion response was recorded as progressive disease.
- Date of last adequate tumor assessment is the date the last tumor assessment with overall lesion response of CR, PR or SD which was made before an event or a censoring reason occurred. In this case the last tumor evaluation date at that assessment is used. If no post-baseline assessments are available (before an event or a censoring reason occurred) the date of randomization/start of treatment is used.
- Date of next scheduled assessment is the date of the last adequate tumor assessment plus the protocol specified time interval for assessments. This date may be used if back-dating is considered when the event occurred beyond the acceptable time window for the next tumor assessment as per protocol (see [Section 14.1.3.2.8](#)).

Example (if protocol defined schedule of assessments is 3 months): tumor assessments at baseline - 3 months - 6 months - missing - missing - PD. Date of next scheduled assessment would then correspond to 9 months.

- Date of discontinuation is the date of the end of treatment visit.
- Date of last contact is defined as the last date the patient was known to be alive. This corresponds to the latest date for either the visit date, lab sample date or tumor assessment date. If available, the last known date patient alive from the survival follow-up page is used. If no survival follow-up is available, the date of discontinuation is used as last contact date.
- Date of secondary anti-cancer therapy is defined as the start date of any additional (secondary) antineoplastic therapy or surgery.

14.1.3.2.8 Handling of patients with non-measurable disease only at baseline

It is possible that patients with only non-measurable disease present at baseline are entered into the study, either because of a protocol violation or by design (e.g. in Phase III studies

with PFS as the primary endpoint). In such cases the handling of the response data requires special consideration with respect to inclusion in any analysis of endpoints based on the overall response evaluations.

It is recommended that any patients with only non-measurable disease at baseline should be included in the main (ITT) analysis of each of these endpoints.

Although the text of the definitions described in the previous sections primarily relates to patients with measurable disease at baseline, patients without measurable disease should also be incorporated in an appropriate manner. The overall response for patients with measurable disease is derived slightly differently according to Table 14-4.

Table 14-4 Overall lesion response at each assessment: patients with non-target disease only

Non-target lesions	New Lesions	Overall lesion response
CR	No	CR
Non-CR/Non-PD ¹	No	Non-CR/non-PD
UNK	No	UNK
PD	Yes or No	PD
Any	Yes	PD

¹ As defined in [Section 14.1.2.4](#)

In general, the **non-CR/non-PD response** for these patients is considered equivalent to an SD response in endpoint determination. In summary tables for best overall response patients with only non-measurable disease may be highlighted in an appropriate fashion e.g. in particular by displaying the specific numbers with the non-CR/non-PD category.

[figure not shown]
In considering how to incorporate data from these patients into the analysis the importance to each endpoint of being able to identify a PR and/or to determine the occurrence and timing of progression needs to be taken into account.

For ORR it is recommended that the main (ITT) analysis includes data from patients with only non-measurable disease at baseline, handling patients with a best response of CR as “responders” with respect to ORR and all other patients as “non-responders”.

For PFS, it is again recommended that the main ITT analyses on these endpoints include all patients with only non-measurable disease at baseline, with possible sensitivity analyses which exclude these particular patients. Endpoints such as PFS which are reliant on the determination and/or timing of progression can incorporate data from patients with only non-measurable disease.

14.1.3.2.9 Sensitivity analyses

This section outlines the possible event and censoring dates for progression, as well as addresses the issues of missing tumor assessments during the study. For instance, if one or more assessment visits are missed prior to the progression event, to what date should the progression event be assigned? And should progression event be ignored if it occurred after a long period of a patient being lost to follow-up? It is important that the protocol and RAP specify the primary analysis in detail with respect to the definition of event and censoring dates and also include a description of one or more sensitivity analyses to be performed.

Based on definitions outlined in [Section 14.1.3.2.7](#), and using the draft FDA guideline on endpoints (Clinical Trial Endpoints for the Approval of Cancer Drugs and Biologics, April 2005) as a reference, the following analyses can be considered:

Table 14-5 Options for event dates used in PFS, TTP, duration of response

[figure not shown]
Situation		Options for end-date (progression or censoring) ¹ (1) = default unless specified differently in the protocol or RAP	Outcome
A	No baseline assessment	(1) Date of randomization/start of treatment ³	Censored
B	Progression at or before next scheduled assessment	(1) Date of progression (2) Date of next scheduled assessment ²	Progressed Progressed
C1	Progression or death after exactly one missing assessment	(1) Date of progression (or death) (2) Date of next scheduled assessment ²	Progressed Progressed
C2	Progression or death after two or more missing assessments	(1) Date of last adequate assessment ² (2) Date of next scheduled assessment ² (3) Date of progression (or death)	Censored Progressed Progressed
D	No progression	(1) Date of last adequate assessment	Censored
E	Treatment discontinuation due to 'Disease progression' without documented progression, i.e. clinical progression based on investigator claim	(1) N/A (2) Date of discontinuation (visit date at which clinical progression was determined)	Ignored Progressed
F	New anticancer therapy given	(1) Date of last adequate assessment (2) Date of secondary anti-cancer therapy (3) Date of secondary anti-cancer therapy (4) N/A	Censored Censored Event Ignored
G	Deaths due to reason other than deterioration of 'Study indication'	(1) Date of last adequate assessment	Censored (only TTP and duration of response)
^{1.} =Definitions can be found in Section 14.1.3.2.7 . ^{2.} =After the last adequate tumor assessment. "Date of next scheduled assessment" is defined in Section 14.1.3.2.7 . ^{3.} =The rare exception to this is if the patient dies no later than the time of the second scheduled assessment as defined in the protocol in which case this is a PFS event at the date of death.			

The primary analysis and the sensitivity analyses must be specified in the protocol. Clearly define if and why options (1) are not used for situations C, E and (if applicable) F.

Situations C (C1 and C2): Progression or death after one or more missing assessments: The primary analysis is usually using options (1) for situations C1 and C2, i.e.

- (C1) taking the actual progression or death date, in the case of only one missing assessment.
- (C2) censoring at the date of the last adequate assessment, in the case of two or more consecutive missing assessments.

In the case of two or missing assessments (situation C2), option (3) may be considered jointly with option (1) in situation C1 as sensitivity analysis. A variant of this sensitivity analysis consists of backdating the date of event to the next scheduled assessment as proposed with option (2) in situations C1 and C2.

Situation E: Treatment discontinuation due to ‘Disease progression’ without documented progression: By default, option (1) is used for situation E as patients without documented PD should be followed for progression after discontinuation of treatment. However, option (2) may be used as sensitivity analysis. If progression is claimed based on clinical deterioration instead of tumor assessment by e.g. CT-scan, option (2) may be used for indications with high early progression rate or difficulties to assess the tumor due to clinical deterioration.

Situation F: New cancer therapy given: the handling of this situation must be specified in detail in the protocol. However, option (1), i.e. censoring at last adequate assessment may be used as a default in this case.

Additional suggestions for sensitivity analyses

Other suggestions for additional sensitivity analyses may include analyses to check for potential bias in follow-up schedules for tumor assessments, e.g. by assigning the dates for censoring and events only at scheduled visit dates. The latter could be handled by replacing in [Table 14-5](#) the “Date of last adequate assessment” by the “Date of previous scheduled assessment (from baseline)”, with the following definition:

- **Date of previous scheduled assessment (from baseline)** is the date when a tumor assessment would have taken place, if the protocol assessment scheme was strictly followed from baseline, immediately before or on the date of the last adequate tumor assessment.

In addition, analyses could be repeated using the Investigators’ assessments of response rather than the calculated response. The need for these types of sensitivity analyses will depend on the individual requirements for the specific study and disease area and have to be specified in the protocol or RAP documentation.

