Visit Name	Category	Reference to Section 7.2	Screening Baseline	Core study																	End of core study/Early withdraw (EOS)	Safety FU visit **
				1	2	3	4	5	6	7	8	9	10	11	12	13	14	15	16	17		
Study Day			-28 to-1	1	15	21	29	49	57	85	113	141	169	197	225	253	281	309	337			
Week				2	3	4	7	8	12	16	20	24	28	32	36	40	44	48	52			
Contact IVRS for randomization			X																			
Pasireotide LAR injections (q28d)	D			X			X		X	X	X	X	X	X	X	X	X	X	X	X	X	X***
Everolimus administration (daily)	D			Daily***																		
Core study completion	D																				X	
*Only for patients treated with pasireotide LAR ** The safety FU visit should be performed only for patients who prematurely discontinue study treatment or experience disease progression at week 52. The visit should be performed 56 days after the last dose of pasireotide LAR or everolimus, whichever comes last. ***Pasireotide LAR injection and everolimus should be given at V18 only to patients that continue the extension phase																						

[figure not shown]
[figure not shown]

Table 7-2 EXTENSION PHASE - Visit evaluation schedule

Visit No.	Category	Reference to Section 7.2	Extension phase					End of extension phase /Early withdrawn	Safety FU visit**
			1	2	3	4			
Month of extension phase			3	6	9	12	Every 3 mos		
Vital signs	D	7.2.2.2	X	X	X	X	X	X	
Physical examination	S	7.2.2.1	X	X	X	X	X	X	
Weight	D	7.2.2.3	X	X	X	X	X	X	
WHO performance status	D	7.2.2.4	X	X	X	X	X	X	
Tumor evaluation, frequency at investigator's discretion***	D	7.2.1.1	X	X	X	X	X	X	
Gallbladder assessment, frequency as per tumor evaluation at investigator's discretion	D	7.2.2.6.4	X*	X*	X*	X*	X*	X*	
Pulmonary Function Test	D	7.2.2.6.2	As medically indicated						
Bronchoscopy	D	7.2.2.6.3	As medically indicated						
Chest X-ray, or Chest CT scan	D	7.2.2.6.1	As medically indicated						
ECG	D	7.2.2.7.1	X	X	X	X	X	X	
Cardiac imaging (ECHO or MUGA scan)	D	7.2.2.7.2	As medically indicated						
Hematology	D	7.2.2.5.1	X	X	X	X	X	X	
Biochemistry	D	7.2.2.5.3	X	X	X	X	X	X	
Fasting glucose/insulin/HbA1c (everolimus monotherapy)	D	7.2.2.5.4	X	X	X	X	X	X	
Fasting glucose/insulin/HbA1c (combination)	D	7.2.2.5.4	X	X	X	X	X	X	
Fasting glucose/insulin/HbA1c pasireotide LAR monotherapy	D	7.2.2.5.4	X	X	X	X	X	X	
Blood glucose self monitoring (if applicable)		7.2.2.5.4	Continuous						
Liver Function Tests	D	7.2.2.5.5	X	X	X	X	X	X	

[figure not shown]

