7.2.1.1.1 Tumor Evaluation

Tumor evaluation (chest, abdomen and pelvis) will be assessed at baseline by means of triphasic CT or MRI. CT scan is the preferred modality and should be used wherever possible. Measurable lesions -i.e., target lesions and the non-target lesions by which subsequent response assessments will be judged- must be identified during tumor assessment at baseline; the disease must be staged and progression confirmed at this time.

The tumor evaluation is to be repeated every 3 months or at EOS if reached earlier. During the extension period, tumor evaluation is recommended every 3 months

All images will be read locally at the site by the reviewer. Clinical decisions will be done locally by the investigator with the local radiologist.

All images will be saved on a CD-rom and locally stored at the site in order to allow any future double check of the tumor assessment, if needed.

Evaluation of the endpoints will be done by a local radiologist together with the investigator.

All patients with bone pain or bone uptake at Octreoscan guided imaging at baseline should repeat the assessment while on treatment (including MRI).

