6.1 Implementation of RECIST

Tumor response and disease progression will be evaluated according to the Novartis guidelines based on RECIST 1.1 criteria (enclosed in protocol Appendix 1), unless otherwise noted.

The evaluation of overall lesion response at each assessment is a composite of the target lesion response, non-target lesion response and presence of new lesions as shown below. This information will be captured on the CRF.

Table 4 - Evaluation of overall lesion response

Target lesions	Non-target lesions	New Lesions	Overall lesion response
CR	CR	No	CR ¹
CR	Non-CR/Non PD	No	PR
CR, PR, SD	UNK	No	UNK
PR	Non-PD and not UNK	No	PR ¹
SD	Non-PD and not UNK	No	SD ^{1,2}
UNK	Non-PD or UNK	No	UNK ¹
PD	Any	Yes or No	PD
Any	PD	Yes or No	PD
Any	Any	Yes	PD

¹ This overall lesion response also applies when there are no non target lesions identified at baseline.
² Once confirmed PR was achieved, all these assessment are considered PR.

A listing of the tumor assessments and responses will be presented for the full analysis set after completion of core phase and extension phase analyses. This will include evaluation number, type of lesion (target, non-target, new), overall assessment, number, location, measurement method, evaluation date, longest diameter (cm), lesion status and an overall lesion response as per the investigator. Patients who discontinue study treatment after 12 months of treatment without evidence of progression or for reasons other than disease progression will continue to have tumor evaluation assessments unless consent is withdrawn. These will be flagged in this listing.

Another listing of lesion locations and descriptions will also be produced for the full analysis set. This will include the evaluation number, the type of lesion (target, non-target, new), the

number, the evaluation date, the location, the description, the measurement method and the measurement method detail.

For each time to event assessment, the assessment date is calculated as follows:

- the latest of all measurement dates for assessment with overall lesion response = CR, PR, SD or UNK.
- the earliest of all measurement dates for assessments with overall lesion response = PD.

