7.1 Progression-free survival (PFS)

The progression-free survival (PFS) is defined as the time from first study drug administration to objective tumor progression or death from any cause (including extension phase data, if applicable at the time of the extension phase analyses). If a patient has not had an event, PFS is censored at the date of the last adequate tumor assessment. PFS will be analyzed in the FAS and PP set (for both core and extension phases) by presenting the Kaplan-Meier curve and estimators.

The Kaplan-Meier estimate of the PFS survival function will be constructed and displayed by treatment arm overall and per stratum for the core phase analyses and extension phase analyses. The plots will also display the number of patients at risk every 3 months. Median PFS for each treatment arm will be obtained along with 95% confidence intervals calculated by SAS procedure LIFETEST using method of Brookmeyer and Crowley (1982). 25% and 75% percentiles will be calculated as well. K-M event-free probability estimates with 95% confidence intervals using the Greenwood formula will be summarized as well at the following time points: 3, 6, 9, and 12 months. This analysis will be repeated for the FAS set after completion of the extension phase and interpreted exploratory. The progression-free survival analysis after extension phase will take into consideration evaluations during extension phase as well, if a patient has not had an event (discontinued for other reason than PD or death or trial was ended), PFS is censored at the date of the patient's last adequate tumor assessment in study.

Time to progression and death will be listed per patient presenting the start and end date of treatment, the progression status (Y/N), progression date, last progression-free date, death status (Y/N), date of death along with principal cause of death and date of last adequate tumor assessment which is used for censoring.

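### Extension scan frequency is discretionary, but the Appendix 1 default, not clearly overridden, censors progression or death after two missing scans, so cumulative PFS can be overstated beyond about month 12

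*Protocol*

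**What the plan says.** In the core phase the scan schedule is fixed (Protocol 7.2.1.1.1): "The tumor evaluation is to be repeated every 3 months or at EOS if reached earlier". In the extension it is softer. The same section says "During the extension period, tumor evaluation is recommended every 3 months", and the row label in Table 7-2 reads "Tumor evaluation, frequency at investigator's discretion", although that table also marks every three-monthly visit.

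Protocol Appendix 14.1.3.2.9 (Table 14-5) lists the options for situation C2, "Progression or death after two or more missing assessments". Option 1 censors at the last adequate scan, option 2 counts an event at the next scheduled scan date, and option 3 counts an event on its actual date. The key to the table gives the status of option 1: "1) = default unless specified differently in the protocol or RAP". The text below it repeats the rule: "C2) censoring at the date of the last adequate assessment, in the case of two or more consecutive missing assessments". The same section requires the protocol to set out the primary and sensitivity analyses and to justify any departure from option 1 in situation C.

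SAP 6.1 evaluates response and progression "according to the Novartis guidelines based on RECIST 1.1 criteria (enclosed in protocol Appendix 1), unless otherwise noted". SAP 7.1 defines the PFS event as "objective tumor progression or death from any cause (including extension phase data", if applicable), and censors patients who have had no event. Neither SAP 7.1 nor Protocol 10.5.2 mentions missed scans. PFS throughout the study is a stated secondary objective, and SAP 3.4.2 reruns it after the extension.

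**The concern.** The C2 rule was built for missed visits on a fixed schedule. In the extension the three-monthly schedule is not mandatory, so an investigator who scans a patient with slow disease every 9 months is within the protocol. If that patient's next scan shows progression, two three-monthly assessments have passed without a scan. A literal reading of the default then discards the progression and censors the patient at the previous scan. A death after two missed scans is lost in the same way, although SAP 7.1 counts death from any cause.

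Such patients add progression-free time, but events found after their long gaps are removed. The censoring depends on the event having been found, so it is informative, and the late part of the Kaplan-Meier curve can only move up. SAP 7.1 reports curves by arm and stratum, medians and quartiles from the cumulative data. With few patients still at risk, a handful of discarded events could move the tail.

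**Working it through.** **The plan's own example.** Appendix 14.1.3.2.7 takes a three-monthly schedule with scans at 3 and 6 months, two missing, then progression. The next scheduled assessment is 6 + 3 = 9 months, as the plan states. If progression is found at the next three-monthly scan, that is month 15. Table 14-5 then gives three answers for one patient: censored at 6 (option 1), event at 9 (option 2), event at 15 (option 3).

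**When the default bites.** Missed scans = gap/3 − 1. A 3-month gap gives 0. A 6-month gap gives 1, which is situation C1, and its default keeps the event. A 9-month gap gives 2 and a 12-month gap gives 3, and both are C2. A patient scanned at month 12 and next at month 21 has missed months 15 and 18, so a progression at month 21 becomes censoring at month 12. The curve up to month 12 does not change.

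**Who is exposed.** The rationale for Protocol Amendment 5 gives 41 of 124 randomized patients entering the extension (41/124 = 33%).

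**Size.** The documents give no scan gaps and no PFS assumptions, so these inputs are assumed: exponential time to event with median 12 months from extension entry, 10% of events deaths, 36 months of extension follow-up, 200,000 simulated patients per scenario, and the gap mixes shown. The true progression-free share 24 months into the extension is 0.5^(24/12) = 25.0%. Option 3 uses actual event dates. Option 2 back-dates after one or more missed scans.

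| Scan gaps (rest 3-monthly) | Events dropped by option 1 | Option 1 | Option 3 | Option 2 |
|---|---|---|---|---|
| all 3 months | 0% | 25.0% | 25.0% | 25.0% |
| all 6 months | 0% | 25.0% | 25.0% | 25.0% |
| 20% at 6, 10% at 9 | 9% | 27.7% | 26.0% | 24.7% |
| 25% at 6, 25% at 9 | 23% | 32.0% | 27.1% | 23.8% |
| 25% each at 6, 9 and 12 | 47% | 42.9% | 27.5% | 24.2% |

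In the three mixed rows, option 1 exceeds option 3 by 27.7 − 26.0 = 1.7, 32.0 − 27.1 = 4.9 and 42.9 − 27.5 = 15.4 points. With a median of 9 months (truth 15.7%), option 1 gives 17.6%, 21.5% and 30.6%, against 16.4%, 17.9% and 17.7% for option 3. With a median of 18 months (truth 39.7%), it gives 42.8%, 47.4% and 58.0%, against 40.8%, 41.8% and 41.8%.

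A simpler mix, with a share of 0, 10, 25 or 50% at 9 months, the rest at 3 and no deaths, agrees. Option 1 gives 25.0, 27.8, 33.0 and 45.4%; option 3 gives 25.0, 26.0, 27.6 and 30.2%; option 2 gives 25.0, 24.5, 24.0 and 23.0%.

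**On the scale the SAP reports.** SAP PFS runs from first dose, so these figures are multiplied by the progression-free share at month 12. If that were 50% (assumed, with all such patients entering the extension), the truth is 0.5 × 25.0 = 12.5%. Option 1 becomes 0.5 × 27.7 = 13.9% in the first mixed row and 0.5 × 42.9 = 21.5% in the last.

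**The case against.** The strongest reply is that C2 option 1 is not the rule in force. For the extension, SAP 7.1 describes the patients to be censored as those without an event, and explains this as having stopped for a reason other than progression or death, or the trial having ended. On that reading every documented progression or death counts, and SAP 7.1 is itself the departure that Table 14-5 allows. The adopting sentence in SAP 6.1 concerns the evaluation of response and progression and does not mention missed scans. Appendix 1 is permissive in tone, and Appendix 14.1.4.5.6 marks this censoring reason as optional. This makes the rule ambiguous but does not settle it. Appendix 14.1.3.2.1 uses the same no-event sentence alongside the C2 default, so that sentence alone is not an override, and the express statement that the appendix requires is absent. Two programmers could produce different curves.

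It can also be said that a scan never planned is not missing. That is fair: the documents do not define a missing assessment when frequency is discretionary. SAP 3.9.1 does expect three-monthly extension visits, so a literal count remains possible.

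A reader might infer that extension PFS is in fact overstated, or biased differently by arm. The documents support neither. Three-monthly scans are recommended, no 9-month gap is shown anywhere, and the gap shares above are assumed.

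Finally, option 3 is not unbiased, because sparse scanning dates progression late. This stands. At 24 months into the extension option 2 is nearer the truth in the mixed scenarios. At 12 months (truth 50.0%) option 3 is nearer, with 50.9, 52.0 and 52.2% against 48.6, 46.2 and 46.5%. In these scenarios the two bracket the true value at both times.

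**Conclusion.** The concern holds in a conditional form. Extension scan frequency is discretionary, the Appendix 1 default would remove real events after long gaps, and the SAP neither clearly adopts nor clearly overrides it. No missed-scan sensitivity analysis is planned, although the appendix requires sensitivity analyses to be specified; PFS is only repeated in the per-protocol set.

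If option 1 is applied, cumulative PFS beyond about month 12 can be biased upward. Under the assumed 12-month median the excess over the truth at 24 months into the extension runs from nil (all gaps 6 months or less), through 2.7 points (10% of patients at 9 months), to 17.9 points (half at 9 or 12 months). It is smaller on the curve from first dose. Option 3 is less biased, with an excess of 1.0 to 2.5 points in the mixed scenarios.

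The reach is limited to at most 41 patients, in an analysis that SAP 3.4 labels exploratory and that feeds no hypothesis test. The Month 9 primary endpoint and the 3-, 6-, 9- and 12-month PFS estimates are essentially unaffected. The median is affected only if it lies beyond month 12. The plan should be corrected, but no conclusion about the primary objective depends on it.

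**What to change.** In SAP 7.1, state that for the cumulative core-plus-extension PFS analysis a documented progression or death is an event on its documented date, whatever the gap since the last scan (Table 14-5, C2 option 3). Then:

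- show option 2 (back-dated to the next scheduled scan) and option 1 as sensitivity analyses, noting that option 3 dates some progressions late and option 2 dates some early;
- define what counts as a missed extension assessment for the analysis, and reconcile the wording of Table 7-2 with Protocol 7.2.1.1.1;
- report by arm the distribution of extension scan intervals and the number of events that option 1 would censor.

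The cost is a few sentences in the SAP, reruns of an existing Kaplan-Meier program, and one descriptive table. Table 14-5 already defines the options and the dates are already collected. The drawback is that some progression dates in the main analysis will be late, and the back-dated analysis shows how much that matters.
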